### Tipping Point Multiple Imputation

The second approach analysis will be a tipping point analysis. This will assess the robustness of the primary endpoint analysis by determining the penalty that, when applied to narsoplimab patients with missing data, renders the primary endpoint p-value non-significant. This analysis requires that the data has a monotone missingness pattern, thus, and as necessary, a partial-imputation method using the MCMC method will be employed as described above for Jump to Placebo.

The penalty to render a non-significant primary endpoint p-value will be determined via search as follows. Let the log scale treatment effect estimate from the primary UPE endpoint analysis be denoted as  $\theta\theta\theta\theta\theta\theta$ , then the set of penalty values,  $\{\delta\delta\delta\delta\}$ , to be evaluated will be  $0.00 \cdot \theta\theta\theta\theta\theta\theta, 0.05 \cdot \theta\theta\theta\theta\theta\theta, \dots, 1.00 \cdot \theta\theta\theta\theta\theta\theta, 1.05 \cdot \theta\theta\theta\theta\theta\theta, \dots, 2 \cdot \theta\theta\theta\theta\theta\theta\theta\theta\theta$ . Hence, the starting penalty is zero and thus reflects the primary endpoint analysis assuming MAR; and the penalty  $1.00 \cdot \theta\theta\theta\theta\theta\theta$  reflects a complete loss of the treatment effect in narsoplimab patients with missing data; and the penalty  $2 \cdot \theta\theta\theta\theta\theta\theta\theta\theta\theta$  reflects a complete reversal of the treatment effect in narsoplimab patients with missing data. For each penalty in the vector  $\{\delta\delta\delta\delta\}$ , missing data in both treatment arms will be imputed as

MAR under placebo and the penalty added to those patients with missing data in the narsoplimab arm. The resulting multiply imputed datasets will be analyzed as per the primary endpoint MMRM model as specified in Section 2.9.2.1 and the results combined using Rubin's rules as described above for Jump to Placebo.

The p-value, treatment effect estimate and 95% CI associated with each penalty will be displayed in a forest plot format to allow identification of the 'tipping point' penalty that renders the primary endpoint analysis p-value non significant.

Example SAS code of the form to perform this second sensitivity analysis is contained in [Appendix 2](#).

It should be noted that there is no need for a two dimensional tipping point approach whereby penalties are applied to both placebo and narsoplimab as the approach described above, i.e. applying a penalty to the narsoplimab arm alone and zero penalty to the placebo arm, will yield identical results. This is the case since, in both approaches, missing data are multiply imputed under placebo in both arms. The only difference is that when a penalty  $\{\delta\delta\delta\}$  is applied only to narsoplimab patients with missing data and a penalty  $\{0\}$  is applied to the placebo patients with missing data, the net penalty is  $\{\delta\delta\delta\}$ ; whereas if a penalty matrix  $(\{\delta\delta\delta\}, \{\delta\delta\delta\}^{TTT})$  is constructed whereby the penalty vector  $\{\delta\delta\delta\}$  is applied to narsoplimab patients with,

$$\{\delta\delta\delta\} = \{0.00, 0.05, 1.00, 1.05, 2.00\}$$

$$\{\delta\delta\delta\} = \{\delta\delta\delta_0, \delta\delta\delta_{0.05}, \dots, \delta\delta\delta_{1.00}, \delta\delta\delta_{1.05}, \dots, \delta\delta\delta_{2.00}\}$$

and, for each element,  $\delta\delta\delta_{iiii}, jjjj = 0, 0.05, \dots, 2$ , of  $\{\delta\delta\delta\}$ , the same, transposed penalty vector,  $\{\delta\delta\delta\}^{TTT}$ , is applied to placebo patients with missing data, then the net penalty on the estimated treatment effect when applying element  $\delta\delta\delta_{iiii}$  to narsoplimab patients and  $\delta\delta\delta_{kkkk}$  to placebo patients with missing data will simply be  $\delta\delta\delta_{iiii} - \delta\delta\delta_{kkkk}$  which is the same as application of a penalty  $\delta\delta\delta_{iiii-kkkk}$  to narsoplimab patients and a penalty of 0 to placebo patients with missing data.

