#### **Jump to Placebo Multiple Imputation**

The first approach will employ a control-based multiple imputation [Ratitch 2011] whereby missing observations in both the narsoplimab and placebo groups are imputed using only data observed in the placebo group; as such, this approach reflects a 'jump to placebo (or reference)' analysis. Imputation of values in the placebo arm will assume missing at random (MAR) while imputation of values in the narsoplimab arm will assume missing not at random (MNAR), i.e. as if the patient had been a member of the placebo arm. This approach does not assume a sustained benefit of narsoplimab treatment after discontinuation and limits a post-discontinuation effect to that of placebo. The approach will be implemented as follows:

- Step 1: Non-monotone missing data will be imputed first based on the MAR assumption and a multivariate joint Gaussian imputation model using Markov chain Monte Carlo (MCMC) method as per the MCMC statement in the SAS® PROC MI procedure. As a result, each imputed dataset will only have missing data at the end of patients' records, (a monotone missing data pattern). The MCMC method in the MI procedure will be used with multiple chains (option CHAIN=MULTIPLE), 100 burn-in iterations, and a non-informative prior. A separate imputation model will be used for each treatment arm. The imputation models will include the randomization stratification factors, baseline log UPE and change in log UPE at each time point. In case of non-convergence or non-estimability issues, a ridge prior and a single model will be considered with treatment arm added as explanatory variable to the model.
- Step 2: The remaining, monotone, missing data will be imputed using sequential regression multiple imputation model estimated based on data from the *placebo arm only*. Each sequential regression model (i.e., for imputation of values at a given time point) will include the stratification factors, baseline log UPE, and all previous values of UPE. Missing values at a given time point in placebo and narsoplimab treatment arms will be imputed from the same imputation model, conditional on patient values observed or imputed at previous time points.
- Step 3: The log change from baseline in UPE to each scheduled post-baseline visit will be calculated, based on observed and imputed data. Each of the imputed complete datasets from Step 2 will be analysed with the same MMRM model used for the primary analysis.

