## APPENDIX 2. TIPPING POINT MULTIPLE IMPUTATION

A tipping point analysis whereby missing data are imputed in the narsoplimab arm with an increasing degree of penalization and thus find the ‘tipping point’, i.e., that degree of penalization that renders a positive p-value for the primary endpoint non-significant.

All imputation steps are as described in [Appendix 1](#) apart from the second step where monotone missing data are imputed for patients randomized to narsoplimab are adjusted using the **ADJUST** and **SHIFT** options:

```
/*SECONDLY APPYING TIPPING POINT IMPUTATION*/
PROC MI DATA=MI_OUT1 SEED = <SEED> NIMPUTE = 1 OUT=MI_OUT2<DELTA>;
  BY_IMPUTATION_ STRAT1 STRAT2;
  CLASS RANDTRT;
  MONOTONE REG (W36 = BASE W12 W24 / DETAILS);
  MNAR ADJUST(W12 / SHIFT = <DELTA> ADJUSTOBS=(RANDTRT =
  'NARSOPLIMAB')) ;
  MNAR ADJUST(W24 / SHIFT = <DELTA> ADJUSTOBS=(RANDTRT =
  'NARSOPLIMAB')) ;
  MNAR ADJUST(W30 / SHIFT = <DELTA> ADJUSTOBS=(RANDTRT =
  'NARSOPLIMAB')) ;
  MNAR ADJUST(W36 / SHIFT = <DELTA> ADJUSTOBS=(RANDTRT =
  'NARSOPLIMAB')) ;
  VAR W12 W24 W36 BASE RANDTRT;
RUN;
```

The value of the penalty <DELTA> is progressively increased and the code re-run for each increase. This generates a series of **MI\_OUT2<DELTA>** datasets. To each of these datasets, steps 3 to 6 as described in [Appendix 1](#) will be applied, thus giving rise to a multiply imputed treatment effect estimate for each value of <DELTA> for narsoplimab vs placebo, along with its SE and CI. These treatment effect estimates and CIs will be plotted in a stacked forest plot format vs <DELTA>. The first value of <DELTA> whereby the CI includes zero will be identified as the tipping point.

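### The tipping-point labels fit own-arm MAR imputation, but the SAP imputes both arms from placebo; Appendix 2 codes neither version, and no penalty is defined for the eGFR slope

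*SAP*

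**What the plan says.** SAP Section 2.9.2.2 sets the penalty unit: "Let the log scale treatment effect estimate from the primary UPE endpoint analysis be denoted as" θ̂. The grid runs from 0 to 2 × θ̂ in steps of 0.05. On its meaning the SAP says: "Hence, the starting penalty is zero and thus reflects the primary endpoint analysis assuming MAR; and the penalty" of 1.00 × θ̂ stands for complete loss of effect in narsoplimab patients with missing data, and 2 × θ̂ for complete reversal.

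The same paragraph then imputes missing data in both arms as "MAR under placebo and the penalty added to those patients with missing data in the narsoplimab arm". The next paragraph repeats that both arms are imputed under placebo. For the Jump to Placebo analysis, which uses that same base, the SAP says "imputation of values in the narsoplimab arm will assume missing not at random (MNAR").

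Appendix 1 restricts its imputation model to placebo observations. Appendix 2, which replaces only the second step of Appendix 1, does not. Its regression is "MONOTONE REG (W36 = BASE W12 W24 / DETAILS"), its variable list is "VAR W12 W24 W36 BASE RANDTRT", and one of its four shift statements begins "MNAR ADJUST(W30 / SHIFT = <DELTA> ADJUSTOBS=(RANDTRT".

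SAP Section 2.9.2.3 and Protocol Section 14.1.10.2 extend the tipping point to both eGFR endpoints by reference only. Protocol Section 14.1.10.1 gives no penalty set.

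**The concern.** The labels and the imputation belong to different analyses. If narsoplimab patients with missing data are imputed from placebo, the zero-penalty row is not the primary MAR analysis. It is the analysis that the SAP itself calls MNAR. Every label above it is then displaced as well.

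The tipping point is one of two planned missing-data analyses for a result that SAP Section 2.9.5 says may support regulatory filings. Its whole content is the position of the tipping penalty against the *primary MAR*, *complete loss* and *complete reversal* markers. If those markers are wrong, the robustness statement is wrong. The code cannot resolve the conflict because it matches neither description. For eGFR, a programmer would have to invent the penalty.

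**Working it through.** **Inputs.** θ = −0.393 on the log scale, as printed, and SD 0.80 or 0.63 (SAP Section 1.3.1); N = 180, 90 per arm. (ln 0.65 is −0.431. Displacements below are in units of θ and do not depend on this; the tipping values do.) eGFR slope difference 3.48 mL/min/1.73 m² per year, and Sxx = 378 for three-monthly visits (SAP Section 1.3.2). Missing rates, dropout timing and within-patient correlation ρ are not in the documents and are assumed.

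**1. What the labels require.** Remaining effect at Week 36 in narsoplimab patients with missing data should be +1, 0 and −1 times θ at k = 0, 1, 2. Own-arm MAR with an adverse shift k × |θ| applied once gives 1 − k, that is +1, 0, −1. The labels are reproduced.

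**2. What the text gives.** Under placebo-based imputation:
- No post-baseline UPE: nothing is carried forward, so the effect is 0 − k, that is 0, −1, −2.
- Weeks 12 and 24 observed, exchangeable ρ, equal effect at all visits: the placebo regression carries forward 2ρ/(1+ρ) of θ. This is 0.67 (ρ = 0.5) or 0.89 (ρ = 0.8), a displacement of 0.33 or 0.11.

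A separate large-sample simulation with dropout spread evenly over the visits (ρ 0.5 or 0.7, single shift) gave +0.46 to +0.63 at k = 0 and −0.37 to −0.53 at k = 1.

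**3. Carry-forward.** Appendix 2 shifts each visit, and Section 2.9.2.2 imputes each visit conditional on values observed or imputed earlier. If shifted values feed later visits, the accumulated shift at ρ = 0.5, k = 1, no post-baseline data, in units of |θ|, is:
- W12: 1
- W24: 1 + 0.5 × 1 = 1.5
- W30: 1 + (1/3)(2.5) = 1.83
- W36: 1 + (1/4)(4.33) = 2.08

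| Base and shift | Dropout | k = 0 | k = 1 (ρ = 0.5 / 0.8) |
|---|---|---|---|
| Label | any | +1 | 0 |
| Own arm, once | any | +1 | 0 |
| Own arm, carried | no post-baseline | +1 | −1.08 / −1.55 |
| Own arm, carried | after Week 24 | +1 | −0.25 / −0.31 |
| Placebo, once | no post-baseline | 0 | −1 |
| Placebo, once | after Week 24 | +0.67 / +0.89 | −0.33 / −0.11 |
| Placebo, carried | no post-baseline | 0 | −2.08 / −2.55 |
| Placebo, carried | after Week 24 | +0.67 / +0.89 | −0.58 / −0.42 |

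**4. Sign.** SAP Table 1 takes narsoplimab minus placebo, so a beneficial θ̂ is negative. Adding 1 × θ̂ or 2 × θ̂ literally gave about +1.5 to +1.7 and +2.5 to +2.6 times θ in the same simulation. The benefit grows and the result never tips.

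**5. Illustrative tipping values.** Assumptions: single shift, adverse direction, 20 imputations, equal missing rate m in each arm; simulation noise about 0.05. Entries are the first k at which the CI includes zero, own-arm / placebo-based. Values above 2 lie off the SAP grid.

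| Dropout, SD | 10% | 20% | 30% |
|---|---|---|---|
| No post-baseline, 0.80 | 3.40 / 2.40 | 1.60 / 0.60 | 0.95 / 0.00 |
| No post-baseline, 0.63 | 4.35 / 3.40 | 2.25 / 1.25 | 1.40 / 0.40 |
| After W24, ρ 0.5, 0.80 | 3.60 / 3.25 | 1.65 / 1.30 | 1.10 / 0.75 |
| After W24, ρ 0.5, 0.63 | 4.45 / 4.10 | 2.25 / 1.95 | 1.50 / 1.15 |
| After W24, ρ 0.8, 0.80 | 3.55 / 3.45 | 1.85 / 1.70 | 1.15 / 1.05 |
| After W24, ρ 0.8, 0.63 | 4.45 / 4.35 | 2.45 / 2.35 | 1.65 / 1.55 |

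With no post-baseline data the expected estimates are θ(1 − mk) and θ(1 − m(1 + k)). At 20% and SD 0.80, k = 1.60 own-arm and k = 0.60 placebo-based both give −0.393 × 0.68 = −0.267, one unit apart. The two readings fall on opposite sides of k = 1 in 2 of 6 cells with no post-baseline data and in 1 of 12 late-dropout cells.

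**6. Appendix 2.** There is no placebo restriction, no treatment term in the W36 regression and no RANDTRT in BY. W30 is shifted but is absent from MONOTONE and VAR. This is a pooled model, a third version.

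**7. eGFR.** θ̂ is a log-UPE effect. Absolute eGFR values enter through Appendix 2's cross-reference to Appendix 1. A constant visit-level shift of 3.48 changes one patient's OLS slope by 12 × Σ(x − x̄) × 3.48 / 378, with x̄ = 13.5 months:
- all eight visits imputed: 0.00
- Week 60 on: 12 × 24 × 3.48 / 378 = 2.65
- Week 96 only: 12 × 10.5 × 3.48 / 378 = 1.16

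None equals 3.48.

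**The case against.** The strongest reply is that little is at risk. Placebo-based imputation tips earlier in every cell above, so a reader who trusts the labels understates robustness. Section 2.9.2.2 plots estimate, CI and p-value at every penalty, and Jump to Placebo is reported separately, so a careful reader could spot the k = 0 row. A full one-unit displacement needs patients with no UPE at Weeks 12, 24, 30 and 36, whereas SAP Table 1 and Protocol Section 8.3.1 keep patients in follow-up after stopping treatment. Appendix 2 is example code, and under the simulated random dropout its pooled model gave +0.46 to +0.64 at k = 0, close to placebo-only. The word penalty itself implies an adverse direction.

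All of that stands on size and direction. None of it makes the labels correct, gives the sign rule or supplies an eGFR penalty.

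Some stronger readings are tempting but unsupported:
- *A fragile result would look robust.* Not through the label error, which works the other way. Only the literal sign reading would do this.
- *Own-arm MAR alone restores the labels.* Only with a single shift; the carried rows above do not match.
- *The tipping values forecast the trial.* The documents give no missing rate.
- *The eGFR figures size an error in the treatment effect.* They are single-patient OLS changes, not random-coefficients estimates.
- *The claim that one-arm penalties suffice ("i.e. applying a penalty to the narsoplimab arm alone and zero penalty to the placebo arm, will yield identical results") undermines the plan.* It is not true in general, for example with unequal missing fractions, but no planned analysis changes. It is a wording note.

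**Conclusion.** The point holds as an internal contradiction in Section 2.9.2.2. The labels describe own-arm MAR with one adverse shift; the stated imputation is placebo-based, so penalty 0 is Jump to Placebo. That conclusion rests on the text alone.

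The size rests on assumptions. With a single shift, displacement is one full unit of θ̂ for patients with no post-baseline UPE and about 0.33 to 0.11 for dropout after Week 24 (ρ 0.5 to 0.8). If visit-wise shifts carry forward, it reaches about two units or more at k = 1. The label error is conservative, and alpha, the primary test and the testing sequence are unaffected. The sign ambiguity, the Appendix 2 mismatch and the missing eGFR rule are separate gaps of specification. All should be closed before the interim unblinding.

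**What to change.** (a) Choose one base. Either impute each arm under MAR from its own arm and keep the three labels, or keep placebo-based imputation, relabel penalty 0 as Jump to Placebo and correct the other two.

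(b) State the penalty as k × |θ̂| in the adverse direction: added to imputed log UPE, subtracted from imputed eGFR. Say whether the shift is applied once after imputation or carried through later visits. The existing labels under own-arm MAR need a single application.

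(c) Make Appendix 2 match. Add W30 to MONOTONE and VAR. Put treatment in BY or in the model, or add the placebo restriction if that base is kept. Replace the four sequential SHIFT statements if the shift is applied once.

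(d) For eGFR, define θ̂ as the slope difference and give a rule that turns it into visit-level shifts growing with time. One example, not the only choice, is the per-year penalty times years since the last observed visit. At 3.48, on the regular metabolic panels at Weeks 12, 36, 48, 72 and 96 (Sxx = 262.8), it changes a patient's slope by 3.48 (all imputed), 2.10 (Week 72 on) or 0.86 (Week 96 only).

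(e) Present any planning-stage tipping values only as illustrations, with missing rate, dropout timing and shift rule stated.

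Cost: SAP wording and example code. Data collection and testing do not change.

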#### 1.3.1. Sample Size for Primary UPE Endpoints

The statistical hypotheses are:

$$H_0: \mu_d = \mu_p,$$

$$H_1: \mu_d \neq \mu_p,$$

where  $\mu_d$  and  $\mu_p$  are the mean change in log-transformed 24-hour UPE from baseline to 36 weeks for narsoplimab and placebo, respectively.

[figure not shown]
Based on IgAN patient registry data from University Hospital Leicester, UK, the log scale standard deviation for the change in UPE from baseline to 9 months in IgAN patients with  $\geq 2$  g/day is estimated to be 0.80. Hypothesizing a treatment effect on UPE of 35% (-0.393 on the log scale), a total  $N = 180$  patients with a baseline UPE  $\geq 2$  g/day need to be randomized on a 1:1 basis to narsoplimab or placebo to provide 95% power to test the stated hypotheses, at the 2-sided 5% alpha level. Data from the preplanned blinded sample size reassessment for UPE at

9 months in the high-risk proteinuria population (baseline UPE  $\geq$  2 g/day) gave blinded logscale SD estimates of 0.63, hence the sample size of N = 180 is supported. Further, with N = 180 patients and with an SD of 0.80, if the hypothesized treatment effect on the UPE primary endpoint is observed then the associated 1-sided p-value will be very low, approximately  $p < 0.001$ ; and with an SD of 0.63 the corresponding p-value would be lower still.

[Inker 2021] has established a strong relationship between treatment effects on UPE at 9 months versus treatment effects on eGFR total slope over 2 years in 12 randomized controlled trials involving 990 IgAN patients with a mean [mean  $\pm$  SD] baseline urine protein of 1.8 [1.2 - 2.6] g/day. These data form the basis of multiple completed and ongoing randomized controlled trials in IgAN and also provide the foundation for the accelerated approval of both sparsentan and busedonide in IgAN patients with a baseline proteinuria of  $\geq$  1.5 g/g (being approximately equal to 2 g/day in a 70 kg patient). These data are therefore equally applicable to the OMS721-IGA-001 study population and trial design.

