**Table 1: Estimands For The Primary and Key Secondary Efficacy Endpoints**

Endpoint	Treatment Policy Estimands
Primary	
Primary UPE Endpoint, Patients With Baseline UPE $\geq 2$ g/day	
 
• Treatment regimens to be evaluated = narsoplimab and placebo
 
• The patient population to be evaluated = FAS of all randomized patients with a baseline UPE <math>\geq 2</math> g/day.
 
• The primary UPE endpoint will be analyzed and formally tested for treatment comparison with first 180 patients in the high-risk proteinuria group through 36 weeks in the FAS population.
 
• Patient-level outcome to be analyzed = log change in UPE from baseline to weeks 12, 24, 30 and 36 post randomization, analyzed via mixed model repeated measures analysis (MMRM).
 
• Intercurrent events handling = all patients will be followed for UPE endpoint attainment regardless of early cessation of randomized treatment or the occurrence of intercurrent events such as the use additional systemic therapies.
 
• The population-level estimate of treatment effect = the difference between narsoplimab and placebo in LSmean UPE log change from baseline to 9 months as extracted from the MMRM analysis.
 

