The restricted maximum likelihood (REML) method in SAS PROC MIXED will be used to fit the model. The treatment difference in the rate of change in eGFR over 2 years will be estimated from the model along with its standard error, 2-sided confidence interval and p-value. The applicable alpha level will be 5% in a 2-sided test. Denoting time as **T**, the SAS code will be of the form;

```
PROC MIXED DATA=Y COVTEST CL;
  CLASS PATIENT RANDTRT STRAT1 STRAT2;
  MODEL Y = T RANDTRT RANDTRT*T STRAT1 STRAT2 STRAT1*STRAT2/ SOLUTION COVB;
  RANDOM INT T / TYPE=UN PATIENT SOLUTION G GCORR;

  ESTIMATE "INTERCEPT NAR"      INTERCEPT 1 RANDTRT 0 1           / CL ALPHA=0.05;
  ESTIMATE "INTERCEPT PCB"      INTERCEPT 1 RANDTRT 1 0           / CL ALPHA=0.05;
  ESTIMATE "INTERCEPT NAR v PCB" RANDTRT 1 -1 T 0 RANDTRT*T 0 / CL ALPHA=0.05;

  ESTIMATE "SLOPE NAR"          T 1 RANDTRT*T 0 1 / CL ALPHA=0.05;
  ESTIMATE "SLOPE PCB"          T 1 RANDTRT*T 1 0 / CL ALPHA=0.05;
  ESTIMATE "SLOPE NAR v PCB"    T 0 RANDTRT*T 1 -1 / CL ALPHA=0.05;

  ODS OUTPUT "ESTIMATES"=EST;
  ODS OUTPUT SOLUTIONF=F;
  TITLE "RANDOM CO-EFFICIENTS ANALYSIS TOTAL SLOPE EGFR";
RUN;
TITLE;
```

Sensitivity analyses for both key secondary efficacy eGFR endpoints will include:

- Jump to Placebo Multiple Imputation
- Tipping Point Multiple Imputation

- COVID-19

with these analyses executed in the same fashion as described for the primary UPE endpoint.

While prior FDA co-authored publications and supportive simulations demonstrate that the use of fixed weights as per [Cui, Hung and Wang \(1999\)](#) are necessary to avoid alpha inflation associated with the SSRE procedure, an exploratory analysis of eGFR will be performed using an unweighted test statistic for the rate of change in eGFR over 2 years in the high-risk proteinuria group as requested by FDA.

Given the limited eGFR data points during the first 12 weeks of the study, the presence of an early, acute effect on eGFR cannot be meaningfully assessed. Nevertheless, mean change eGFR data will be presented by treatment groups at all sampling timepoints during the 2-year follow-up study period.

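### As printed, the tipping-point penalty shifts imputed narsoplimab UPE values towards benefit, which contradicts the SAP's own description of that penalty

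*SAP*

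**What the plan says.** SAP Section 2.9.2.2 (Tipping Point Multiple Imputation) ties the penalty to the estimated effect: "Let the log scale treatment effect estimate from the primary UPE endpoint analysis be denoted as" theta-hat. The grid runs from 0.00 to 2 times theta-hat in steps of 0.05. For each value, missing data in both arms are imputed as "MAR under placebo and the penalty added to those patients with missing data in the narsoplimab arm".

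The section gives three points on the grid a meaning:
- Multiple 0: "the starting penalty is zero and thus reflects the primary endpoint analysis assuming MAR".
- Multiple 1.00: it "reflects a complete loss of the treatment effect in narsoplimab patients with missing data".
- Multiple 2: it "reflects a complete reversal of the treatment effect in narsoplimab patients with missing data".

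The sign of theta-hat is fixed elsewhere. SAP Table 1 defines the effect as "the difference between narsoplimab and placebo in LSmean UPE log change from baseline to 9 months". Section 1.3.1 gives the planning value as negative: "Hypothesizing a treatment effect on UPE of 35% (-0.393 on the log scale").

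Appendix 2 passes a value DELTA to the SHIFT option for narsoplimab records and steps it upward. It names the first DELTA whose confidence interval covers zero as the tipping point. Neither Section 2.9.2.2 nor Appendix 2 shows a minus sign or an absolute value on the penalty. Section 2.9.2.3 lists the same sensitivity analyses for both eGFR endpoints, "with these analyses executed in the same fashion as described for the primary UPE endpoint". Protocol Section 14.1.10.1 states the purpose of the analysis but gives no formula.

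**The concern.** A tipping-point penalty has to move imputed values in the active arm against the drug. Here a non-negative multiple of a negative effect is added to the log UPE change, so imputed UPE falls as the multiple rises. The printed rule therefore works against its own name and its own labels.

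This is one of two missing-data robustness checks for the primary endpoint and for both key secondary endpoints. If the printed formula were programmed, the forest plot would show the result strengthening as the supposed penalty grew, and that could be reported as robustness to missing data.

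**Working it through.** **Inputs from the SAP.** Theta = -0.393, SD 0.80 (planning) and 0.63 (blinded estimate), 180 patients randomized 1:1 (Section 1.3.1); c = 0 to 2 (Section 2.9.2.2). **Assumed.** The missing fraction m, because the documents give none; 10% to 30% is shown. Section 1.3.1 pairs -0.393 with a 35% reduction, whereas ln(0.65) = -0.431. That is a separate discrepancy and does not affect the sign.

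**Step 1: can the labels be reproduced?** The effect against placebo in narsoplimab patients with missing data is e = b + s × c × theta. Here b = 0 if imputation is under placebo and b = theta if it is under the patient's own arm; s = +1 as printed and -1 reversed.

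| Base | Sign | c = 0 | c = 1 | c = 2 |
|---|---|---|---|---|
| SAP labels | | -0.393 | 0 | +0.393 |
| Placebo | as printed | 0 | -0.393 | -0.786 |
| Own arm | as printed | -0.393 | -0.786 | -1.179 |
| Placebo | reversed | 0 | +0.393 | +0.786 |
| Own arm | reversed | -0.393 | 0 | +0.393 |

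Only the reversed sign on the own-arm base matches all three labels. The printed sign fails at c = 1 and c = 2 on either base. Reversing the sign while keeping the placebo base still misses all three.

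**Step 2: effect on the test.** Overall effect = (1 - m) × theta + m × e. Illustration: theta = -0.25, m = 20%, SE = 0.63 × sqrt(4/180) = 0.094 held fixed, placebo base.
- As printed: c = 0 gives 0.8 × (-0.25) = -0.20 (p = 0.033); c = 1 gives -0.20 + 0.2 × (-0.25) = -0.25 (p = 0.008); c = 2 gives -0.30 (p = 0.001).
- Reversed: c = 1 gives -0.20 + 0.2 × 0.25 = -0.15 (p = 0.11).

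**Step 3: range of missingness.** Theta = -0.393, SD 0.80, placebo base, with the variance allowed to change: [2 × SD² + m(1 - m)(e - theta)²] / [90(1 - m)].

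| m | As printed, p at c = 0, 1, 2 | Reversed, p at c = 0, 1, 2 |
|---|---|---|
| 10% | 0.005, 0.002, 0.0006 | 0.005, 0.014, 0.037 |
| 20% | 0.020, 0.003, 0.0005 | 0.020, 0.088, 0.28 |
| 30% | 0.057, 0.006, 0.0004 | 0.057, 0.29, 0.80 |

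As printed, p falls along every row. At 30% missing the analysis is already non-significant at c = 0.

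**Step 4: simulation.** A simplified version was run: Week 36 ANCOVA in place of the MMRM, 20 imputations, Rubin's rules, 150 trials per setting, both bases, both SDs, m = 10%, 20% and 30%. As printed, 0 of 1504 trials that were significant at c = 0 became non-significant anywhere on the grid. With the sign reversed, 810 of 1470 did.

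**Step 5: eGFR.** In the Section 2.9.2.3 model, beta-3 is the narsoplimab-minus-placebo slope difference, positive when the drug works, so adding multiples of it raises eGFR. In the SAS code of that section, the narsoplimab slope is coded 0 1 and the placebo slope 1 0. On that coding the comparison contrast 1 -1 is placebo minus narsoplimab, which has the opposite sign. Appendix 1 imputes absolute eGFR values, so a slope difference has no defined meaning as a shift until it is multiplied by time.

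**The case against.** The best defence is that the intent is plain. The words penalty, loss and reversal all point the adverse way. A DELTA stepped upward from zero, as in Appendix 2, is positive and raises imputed log UPE, which is adverse. The forest plot required for every penalty would also expose p-values that fall as the penalty rises. This stands as far as it goes: a programmer who follows Appendix 2 for UPE may well get the right direction. But Appendix 2 never states the sign of DELTA, and Section 2.9.2.2 sets its values as multiples of a negative number. The same upward-stepped DELTA would be favourable for eGFR.

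A minus sign or absolute-value bars might also have been lost from the PDF text, where theta is garbled. This cannot be fully excluded. However, minus signs survive in Section 1.3.1 and in the net-penalty expression of Section 2.9.2.2, and absolute-value bars would not help eGFR, where adding a positive amount is a benefit.

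Two stronger readings are tempting, and the documents do not support them:
- **The analysis can never tip and must report full robustness.** Imputation is under placebo, so the zero-penalty result is already diluted and can itself be non-significant; Appendix 2 would then report tipping at DELTA = 0. With an estimate of -0.20, 10% missing and SE 0.094, p is 0.033 in the primary analysis and 0.055 (effect -0.18) at c = 0. In the simulation on the placebo base, 6 of 130, 27 of 122 and 48 of 125 primary-significant trials were non-significant at c = 0 (SD 0.80; 10%, 20% and 30% missing).
- **The eGFR shift is favourable throughout.** The model and the code give opposite signs, so the direction is undetermined rather than uniformly wrong.

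**Conclusion.** The rule in Section 2.9.2.2 is wrong as printed for log UPE: it adds a benefit where it describes a penalty, and it cannot produce its own loss and reversal labels. No non-zero penalty on the printed grid can turn a result that is significant at zero penalty non-significant. That follows algebraically when the standard error is held fixed, and it held in every simulated trial when the standard error was allowed to vary. For eGFR the direction and scale are unspecified.

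The sign conclusion needs no assumption beyond theta-hat being narsoplimab minus placebo, which Table 1 and Section 1.3.1 support. The p-values rest on assumed missingness, an illustrative estimate of -0.25 and a normal approximation. The primary test itself is unaffected. What is at stake is whether a supportive robustness analysis can do its job.

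**What to change.** 1. In Section 2.9.2.2, define delta = -c × theta-hat, c = 0, 0.05, ..., 2, with theta-hat stated to be narsoplimab minus placebo.
2. In Appendix 2, state that SHIFT is positive (adverse) for log UPE and negative (adverse) for eGFR.
3. Impute the narsoplimab arm under its own-arm MAR model before the shift, so that c = 0, 1 and 2 mean what the section says. If the placebo base is kept, rewrite the three labels instead. The Appendix 2 example code lacks the placebo-only restriction used in Appendix 1, so the chosen base must be stated there too.
4. For eGFR, settle the direction of the slope contrast in Section 2.9.2.3 and scale the shift by time, for example -c × slope difference × time at each visit.

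The cost is a short SAP amendment: a line for the sign, a sentence on the base, a short paragraph for eGFR, and matching code. It does not change trial conduct, sample size or the primary analysis. It should be made before the interim database snapshot, by which time Protocol Section 14.1.4 requires the SAP to be final.
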